The concentrated preserved samples will be shaken gently for proper mixing from which 1 ml sub-sample will be drawn by pipette and transferred into a Sedgewick-Rafter (S-R) counting cell following the standard procedures (APHA, 1998). The samples will then be placed under a compound binocular microscope at a magnification of 10x, 40x or 100x and then observed for identification and enumeration. The phytoplankton will be identified following the procedures described by various authors (Smith, 1950; Ward & Whipple, 1959; Desikachary, 1959; Needham and Needham, 1961; Islam and Khatun, 1966, Islam and Nahar, 1967; Islam *et al.*, 1992; Prescott, 1984; Khondker and Parveen, 1992; APHA, 1998).

After identification of phytoplankton in each sample, they will then be enumerated to study their abundance. A number of strips (sub-cells) of S-R cell will be randomly examined for each sample. The total numbers of phytoplankton will be estimated by the formula given below.

$$N = \frac{C \times 1000\text{mm}^3}{L \times D \times W \times S} \times F$$

Here,

N = Total number of phytoplankton per litre of original water.

C = Average number of phytoplankton observed.

L = Length of a strip (sub-cell) of S-R cell = 1 mm.

D = Depth of strip of S-R cell = 1 mm.

W = Width of strip of S-R cell = 1 mm.

S = Number of counted strips of the S-R cell.

F = Volume of sample concentrated from 1 litre original sample.

C:\Protocol\Mozambique\Revised protocol - Mozambique

Thus the formula can be summarized as follows:

$$N = \frac{C \times 1000\text{mm}^3}{S} \times F$$

Zooplankton

One hundred liters or an appropriate volume of water (depending on concentration) will be filtered through 60µm mesh size plankton net (Millipore, Ges.m.b.H, [name], Cat# NY6000010) and the concentrated samples will be collected in 4oz glass bottles. The samples will be brought to the laboratory within 24 hours after collection in an insulated icebox using cool packs to maintain the temperature at 4°C. The collected zooplankton samples will further be concentrated by the plankton net so that the ultimate volume of the concentrated sample become 50 ml. The concentrated zooplankton samples from different sites will be kept in separate scintillation glass vials and will be preserved by adding 4% formalin. Then the samples will be kept for identification and enumeration.

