The preserved samples will be shaken gently for proper mixing from which 1ml sub- samples will be drawn by pipette and transferred into a Sedgewick-Rafter (S-R) counting cell following standard procedure (APHA, 1998). The samples will then be placed under a compound binocular microscope at a magnification of 10X and then observed for identification and enumeration. The magnification of the compound microscope are sometimes adjusted to 4X, 40X or 100X according to the need for better observation and identification. The zooplanktons are identified by using the taxonomic keys, identifying characteristics and specific figures following Ward & Whipple (1959), APHA (1998), Needham & Needham (1961), Bhouyain & Asmat (1992) and other relevant literatures.

After identification of zooplankton in each sample, they will then be enumerated for their abundance. At least a total of 100 strips (sub-cells) of S-R cell will randomly examined for each sample and the zooplankton lying within that area will be counted for each species, genera, group and phylum wise. The total numbers of zooplankton will be estimated following the formula described above for phytoplankton.

Water

One liter water sample will be collected from each sampling site in a one liter capacity Nalgene (Nalgene company, USA) plastic bottle. This water will be collected after passing through a 20-µm mesh size Millipore plankton net to make water free from zooplankton and phytoplankton. This water will be used for both microbiological and chemical analyses.

Culture of *V. cholerae* from zooplankton, phytoplankton and water

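### The plankton density formula divides by the number of strips although its count is defined as an average, and it is reused for zooplankton without restating F for the litres filtered; densities can be wrong by a factor that varies between samples.

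*Protocol*

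**What the plan says.** All references are to the Protocol, Research Design and Methods, Sample collection and Processing, unless stated.

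**Phytoplankton.** One litre of water is concentrated, a 1 ml sub-sample goes into a Sedgewick-Rafter cell, and strips are counted: "A number of strips (sub-cells) of S-R cell will be randomly examined for each sample". Density is N = C × 1000 mm³/(L × D × W × S) × F, with these definitions:

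- The target is a density, given as "N = Total number of phytoplankton per litre of original water".
- The count in the numerator is an average with no unit attached: "C = Average number of phytoplankton observed".
- The strip dimensions are fixed, as in "L = Length of a strip (sub-cell) of S-R cell = 1 mm"; both D and W have the same value.
- The divisor counts strips: "S = Number of counted strips of the S-R cell".
- The concentration term is tied to one litre: "F = Volume of sample concentrated from 1 litre original sample".

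**Zooplankton.** The volume sampled is different and variable: "One hundred liters or an appropriate volume of water (depending on concentration) will be filtered". The catch is reduced to 50 ml, and a minimum of 100 strips is examined. Then: "The total numbers of zooplankton will be estimated following the formula described above for phytoplankton". F is not redefined, and no symbol stands for the litres filtered.

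**Use of the data.** The Data Analysis section plans a Pearson correlation of phytoplankton and zooplankton with *V. cholerae*, and a comparison of the Bangladesh and Mozambique data. Under Activities in Mozambique, the Beira laboratory is to follow the methods set out for Bangladesh.

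**The concern.** Two definitions do not fit the formula they serve.

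First, a divisor S converts a total over S strips into a count per strip. If C is already an average per strip, the division is made twice. The unit of the average is not stated, but strips are the only repeated unit described for a sample.

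Second, F is tied to 1 litre of original water. That fits the phytoplankton bottle. For zooplankton, the only concentrate volume given is 50 ml, and it comes from about 100 L or some other volume. An analyst who enters 50 for F leaves the litres filtered out of the calculation.

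If S and V were the same for every sample, each slip would be a constant factor and would not change a Pearson correlation within one plankton type. The Protocol does not hold them constant. V is chosen according to concentration, so an error that depends on V may also be related to true density. Two laboratories that read the definitions differently would also produce a country difference that is pure arithmetic.

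**Working it through.** **Inputs from the Protocol.** L = D = W = 1 mm, so one strip is 1 mm³ and the 1 ml cell holds 1000 strips. Zooplankton concentrate is 50 ml, V is 100 L or another volume, and S is at least 100. Phytoplankton S is not fixed.

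**Assumed for illustration.** True phytoplankton density 50,000/L with F = 100 ml (the size of the collection vial); true zooplankton density 200/L; V from 10 to 200 L; S from 10 to 1000.

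**The plan's own figure.** No numerical density is given, so there is none to reproduce. The one step that can be checked, the simplification to N = C × 1000/S × F, is correct: with C = 37, S = 40 and F = 100, both forms give 92,500.

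**Phytoplankton.** The concentrate holds 50,000/100/1000 = 0.5 organisms per strip.

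- C as total over S = 100 strips: C = 50, and N = 50 × 1000/100 × 100 = 50,000. This is correct, and it is correct at any S.
- C as mean per strip: C = 0.5, and N = 0.5 × 1000/S × 100 = 50,000/S.

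| S | N with C as mean per strip | Ratio to truth |
|---|---|---|
| 10 | 5,000 | 0.1 |
| 20 | 2,500 | 0.05 |
| 100 | 500 | 0.01 |
| 1000 | 50 | 0.001 |

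Identical waters counted on 20 and on 100 strips would differ by 2,500/500 = 5-fold.

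**Zooplankton.** At V = 100 L the concentrate holds 200 × 100/50/1000 = 0.4 per strip, or 40 in 100 strips.

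- (a) C total, F = 50: 40 × 1000/100 × 50 = 20,000/L, 100 times too high.
- (b) C mean per strip, F = 50/100 = 0.5: 0.4 × 1000/100 × 0.5 = 2/L, 100 times too low.
- (c) C mean per strip, F = 50: 0.4 × 1000/100 × 50 = 200/L, correct because the two slips cancel.
- (d) C total, F = 0.5: 40 × 1000/100 × 0.5 = 200/L, correct.

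In general the ratio to the truth is V for (a), 1/S for (b), V/S for (c) and 1 for (d):

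| V (L) | S | (a) | (b) | (c) | (d) |
|---|---|---|---|---|---|
| 100 | 100 | 100 | 0.01 | 1.0 | 1.0 |
| 100 | 200 | 100 | 0.005 | 0.5 | 1.0 |
| 10 | 100 | 10 | 0.01 | 0.1 | 1.0 |
| 200 | 100 | 200 | 0.01 | 2.0 | 1.0 |

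**Effect of a variable V.** Take case (a), and assume that sparse water is filtered in larger volumes. A site at 10/L with V = 200 L gives 10 × 200 = 2,000/L. A site at 200/L with V = 10 L gives 200 × 10 = 2,000/L. A true 20-fold difference disappears.

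**The case against.** The strongest reply is that both problems depend on the reading. The definition of C does not say per strip. If C were the mean of total counts from repeated examinations of S strips, the formula would be right. The zooplankton text gives this some support: it mentions sub-samples in the plural and describes counting everything within the examined area. Likewise, F is defined per litre. Taken literally, zooplankton F is 50/V, or 0.5 ml per litre at 100 L, and with C as a total the formula returns the true density. Both replies stand, so each defect is an ambiguous definition and not a proven miscalculation. They do not remove the point: no replicate counts are described, and 50 ml is the only zooplankton concentrate volume the text offers.

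A reader might infer three stronger things that the Protocol does not support.

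- *That the error is at most 100-fold.* It has no such bound. The 100 strips are a minimum, so the strip error alone would be at least 100-fold for zooplankton and 1000-fold if the whole cell is counted. At the stated 100 L and 100 strips the two slips together cancel.
- *That every sample carries a different factor.* The factor can differ when S or V differs; nothing says that it always does.
- *That the aim on plankton as a habitat of *V. cholerae* collapses.* That aim rests largely on detecting the organism in plankton samples by culture and fluorescent antibody. The logistic regression of presence and the McNemar comparison of methods do not use N. The Data Analysis section also does not say which plankton measure enters the Pearson correlation.

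**Conclusion.** The point holds as a defect in a formula that the Protocol itself states. On the natural reading of C, density is understated S-fold. If 50 ml is entered as F, zooplankton density is overstated V-fold. If both happen, the net factor is V/S, which is 1 at 100 L and 100 strips and departs from 1 when V and S differ.

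The first conclusion assumes that the average is per strip, the second that F is not converted to a per-litre value. Because S and V may vary between samples and laboratories, the bias need not be constant. It could distort abundance comparisons between sites and countries, and the plankton–*V. cholerae* correlation if density is the measure used. Analyses of presence or absence are unaffected. The definitions should be settled before sampling starts, because S and V may not be recoverable later if they were not recorded.

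**What to change.** 1. Define C as the total number of organisms counted over all S strips. Alternatively, keep C as the mean per strip and remove S from the formula.
2. Define F, for both plankton types, as final concentrate volume (ml) divided by litres of water concentrated. For phytoplankton this leaves the present meaning unchanged, because one litre is used; for zooplankton it is 50/V.
3. Record S and the litres filtered for every sample, in both laboratories.

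With the total-count definition the formula returned the true density in every case tried (V from 10 to 200 L, S from 100 to 1000). The cost is two redefinitions and two recorded fields, with no extra sampling. A minimum S for phytoplankton and a worksheet shared by Dhaka and Beira would be good practice, but they are optional and not part of the correction.

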At 15-day intervals, various environmental samples will be collected including water, phytoplankton and zooplankton for three years. A three-year study will provide the data needed to obtain statistically valid results and conclusions. One-time sampling will be done for consecutive ten days and weekly for one month to find out whether there is any day-to-day or weekly variation in pathogen load. As we plan to collect sample every 15 days interval, 26 samples from each kind from each site will be collected in a year. Apart from being logistically feasible, this sample size will permit us to demonstrate two-log reduction in the count of microbes in each site. Two water systems (one lentic and one lotic) at Matlab will be selected for sampling. A total of 468 (26 X 2 X 3 =156 each of phytoplankton, zooplankton and water) samples will be collected. All the samples will be transported to Dhaka and will be processed within 24 hours of collection. Culturable and VBNC *V. cholerae* O1 and O139 will be isolated, counted and detected following conventional culture, colony blot and fluorescent antibody techniques. The procedures to be followed are described below:

Sample collection and Processing

Phytoplankton

One litre water from aquatic environment will be collected in a 1 litre capacity narrow mouth Nalgene plastic bottle with 3 ml Lugol's iodine solution for the qualitative and quantitative analysis of phytoplankton. Bottles will be kept in a dark undisturbed place at room temperature for 48 to 72 hours for sedimentation of phytoplankton. Concentrated phytoplankton will carefully be collected from the bottom of the bottles in 100ml vials. If the abundance is low, the phytoplankton will be concentrated by passing through plankton net of mesh size 20µm and then will be kept in a 4-oz bottle. The concentrated phytoplankton samples will be preserved by adding 4% formalin. Then the samples will be kept for identification and enumeration.

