Zooplankton and phytoplankton samples will be collected using 64 µm and 20 µm mesh sizes plankton net respectively. Then the plankton will be homogenized using Sted Fast homogenizer (Fisher Scientific Co.). A portion of the homogenized materials will be inoculated into alkaline bile peptone enrichment media and incubated overnight and then plated onto thiosulphate citrate bile salt sucrose (TCBS) agar and tellurite taurocholate gelatin agar (TTGA). The inoculated plates will be incubated at 37°C for 18 to 24 hours. Vibrio-like organisms (from colony appearance) will be picked up and streaked on gelatin agar medium (Monsur, 1961) and incubated at 37°C to determine the production of gelatinase and will be inoculated into Kliglers Iron Agar (KIA) and Motility Indole Urea (MIU) agar. Presumptive vibrio isolates will be checked for lysine and ornithine decarboxylase, arginine dihydrolase and for fermentation of mannitol, sucrose, mannose and arabinose and growth in 0.3, 8 and 10% NaCl. Serology will be done if indicated. Isolation and

identification of *V. cholerae* O1 and O139 will be carried out following the procedures described by Islam *et al.* (1990a, 1990b, 1994b).

Three hundred milliliter of water sample will be filtered through 0.20 µm Millipore filter paper and the filter paper will be enriched in alkaline bile peptone in 120 ml glass bottle and will be incubated overnight at 37°C. Then the rest of the procedures will be followed as described above.

Direct Fluorescent Microscopy (DFA)

All the samples will be tested for both *V. cholerae* O1 and O139 by fluorescence microscope following the procedures described by Hasan *et al.* (1994, 1995). The procedures are briefly described below.

A thin smear of 5-µl of resuspended sample will be prepared on a well. Controls will be run simultaneously. 5-µl of absolute ethanol will be added in control or sample well to fix the smear, again will be air dried. 10-µl of reconstituted DFA reagent will be added to each well. The slides will be placed in a covered, moist

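### The 20 µm 'phytoplankton' culture sample also retains zooplankton, and low-abundance phytoplankton counts are concentrated in a way that loses cells under 20 µm

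*Protocol*

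**What the plan says.** The relevant text is in the Protocol's Research Design and Methods, under Sample collection and Processing and the culture section that follows.

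- **Culture of V. cholerae from zooplankton, phytoplankton and water:** the sentence that opens "Zooplankton and phytoplankton samples will be collected using" assigns the 64 µm net to the first group and the 20 µm net to the second. The plankton is then homogenised and part of it goes into enrichment broth. No step between netting and homogenising is described.
- **Water:** "This water will be collected after passing through a 20-µm mesh size Millipore plankton net to make water free from zooplankton and phytoplankton".
- **Phytoplankton (counting):** one litre is fixed and left to settle for 48 to 72 hours. The one exception uses a 20 µm mesh: "If the abundance is low, the phytoplankton will be concentrated by passing through plankton net of mesh size". No threshold for low abundance is given.
- **Phytoplankton (formula):** one Sedgewick-Rafter count and one density formula apply to all samples.
- **Zooplankton (counting):** 100 litres, or another suitable volume, "will be filtered through 60µm mesh size plankton net". The culture section gives 64 µm.

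Activities in Mozambique applies the same procedures in Beira.

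**The concern.** Aim 2 asks what role phytoplankton and zooplankton play as habitat for *V. cholerae*. The Background treats a water source as a potential reservoir when the organism is found with both blue-green algae and copepods. The Phase II paragraph makes the cloth-filter intervention conditional on both plankton groups acting as reservoirs. Each of these needs a phytoplankton result that does not simply repeat the zooplankton result. If animals are in the phytoplankton homogenate, an association with copepods alone could satisfy both parts of the criterion. No later analysis can recover an attribution that was lost at the homogeniser.

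The counting problem is different in kind. The concentration method depends on the quantity being measured, so any loss falls only on sparse samples. These densities feed the seasonal comparison and the planned correlation with *V. cholerae*.

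**Working it through.** The protocol states no figure for this point, so there is none to reproduce. The check compares the meshes and then shows two ranges whose unknowns are assumed.

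**Step 1: what each sample holds.** A net keeps what is larger than its mesh.

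| Sample | Stated step | Plankton held |
|---|---|---|
| Zooplankton, culture | 64 µm net | above 64 µm |
| Phytoplankton, culture | 20 µm net, no prior screen stated | above 20 µm, including all above 64 µm |
| Water | filtrate of a 20 µm net | below 20 µm only |
| Zooplankton, count | 60 µm net | above 60 µm |
| Phytoplankton, count, usual | sedimentation of 1 litre | no mesh cut-off |
| Phytoplankton, count, low abundance | 20 µm net | above 20 µm only |

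The second row contains the first. The Water section agrees, since it uses the 20 µm net "to make water free from zooplankton and phytoplankton".

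**Step 2: attribution of a positive culture.** Let *a* be the probability that the algal material in the 20 µm catch yields *V. cholerae*, and *z* the probability that the animals in that catch do. Assuming independence,

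P(phytoplankton culture positive) = 1 - (1 - a)(1 - z).

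With a = 0 this equals z, so positives occur even if algae carry nothing. The observed rate does not identify *a* unless *z* is known or made negligible.

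*z* depends on the water volume behind each catch, and plankton culture volumes are not stated. The only plankton volumes given are for counting: 1 litre for phytoplankton and 100 litres for zooplankton. If culture volumes had that ratio, the phytoplankton sample would be expected to hold 1/100 = 1% as many animals above 64 µm as the zooplankton sample. With equal volumes it would hold as many (100%). Animals of 20 to 64 µm come on top in either case. The carry-over therefore runs from slight to complete, and the documents do not narrow it.

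**Step 3: loss in low-abundance counts.** Let q be the share of cells under 20 µm. The documents give no size distribution, so q is assumed. Netted density / sedimented density = 1 - q, and the understatement factor is 1/(1 - q).

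| q (assumed) | Netted / sedimented | Understatement |
|---|---|---|
| 0.2 | 0.8 | 1/0.8 = 1.25 |
| 0.5 | 0.5 | 1/0.5 = 2 |
| 0.9 | 0.1 | 1/0.1 = 10 |

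The loss is the same whether the net receives raw water or the settled concentrate. The density formula has no term that corrects it. If a sedimented bloom sample is truly R times denser than a netted sparse one, the reported ratio is R/(1 - q). With no threshold for low abundance, two similar samples can also differ by that factor only because they took different routes.

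**The case against.** - **Silence is not a stated procedure.** The culture section lists two meshes and neither describes nor excludes serial filtration, and the laboratory may already filter in sequence. That is possible, but the written method is what will be transferred to Beira, and followed literally it gives overlapping catches.
- **Aim 2 does not say 'separate roles', and a cloth filter removes both groups together.** This is fair, and it limits the practical damage. The reservoir criteria nevertheless name both groups, so a phytoplankton result driven by copepods still misinforms them.
- **Microscopy identifies organisms by eye.** This protects the plankton counts from carry-over. It does not help the culture results. The fluorescent antibody section does not say that the organism carrying the bacteria will be recorded.
- **Size fractions are not taxonomic groups.** This is correct, and it is a real limit of the remedy.

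Three stronger readings are tempting but not supported.

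- A reader might take the equal yields in Table 1 (12 isolates from 1923 samples for each plankton type) as evidence of carry-over or as its upper limit. The netting behind that earlier series is not described and the new culture volumes are unknown, so the table shows neither.
- A reader might infer that the switch to netting inflates the correlation with *V. cholerae*. Data Analysis names Pearson's method with no log transformation. On raw counts the coefficient is governed largely by the high values, which are untouched. On log counts, stretching the low end could weaken it. The direction is not established.
- A reader might say that sparse samples are counted by a different method. Only the concentration step differs; the counting cell and formula are the same.

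**Conclusion.** The point holds in two limited parts. First, with the nets used as written, a positive phytoplankton culture cannot be attributed to algae rather than zooplankton. This follows from the stated meshes and the absence of screening or sorting before homogenising. How often it would mislead depends on culture volumes the protocol does not give. Second, low-abundance phytoplankton densities are understated relative to the others by 1/(1 - q). That is 1.25 to 10 times for assumed q of 20% to 90%, and it distorts the seasonal contrast in density. The 60 µm and 64 µm zooplankton meshes are a minor inconsistency with no shown effect on results. The first part should be settled before sampling starts, because homogenised material cannot be re-sorted.

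**What to change.** 1. Filter in sequence: collect zooplankton on the coarse net, pass that filtrate through the 20 µm net, and use the final filtrate as water.
2. Use equal water volumes for the two plankton culture samples, or record the volume of each.
3. Report culture results by size fraction (above 64 µm, 20 to 64 µm, below 20 µm). Note the microscopic composition of each plankton fraction, from a portion set aside before homogenising.
4. Concentrate every phytoplankton count sample by sedimentation. When abundance is low, settle to a smaller volume or count more sub-cells.
5. Reconcile the 60 µm and 64 µm meshes so that counting and culture use the same zooplankton net, and adjust the fraction limits to match.

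The nets are already planned, so the cost is a little more handling and microscopy. The limit is that size only approximates taxonomy: animals of 20 to 64 µm will sit with the algae and large colonial algae with the zooplankton. That is why the composition should be noted and the fractions named by size.
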